HLH Improvement	 At least 3 of the HLH parameters that were abnormal at baseline must be normalized or improved (i.e., >=50% change from baseline). The remaining may be the same or worse as baseline (unless 2 or more parameters no longer meet the definition of normality) In the case where a patient has only 2 abnormal HLH features at baseline, a change from baseline greater than 50% for both will define HLH as improved. 	 Definition of 50% improvement from baseline: Spleen size decreased by 50%, as recorded in cm from costal margin at physical examination. Absolute Neutrophil Count increased by 50%, if G- CSF has not been administered in the previous 4 days and Platelet count increased by 50%, if no platelet transfusion has been administered in the previous 4 days Ferritin decreased by 50% Fibrinogen increased by 50% or D-Dimer decreased by 50% Normalization of CNS abnormalities = normal neurological assessment by investigator without findings in brain imaging (Brain MRI/Brain CT/cranial ultrasound), CSF analysis or AEs indicative of "CNS involvement" or "CSF abnormalities" 	
No Response	If a subject does not meet the criteria for at least HLH improvement, response is categorized as "No Response"		
Abbreviations: CNS, central nervous system; CSF, cerebrospinal fluid; G-CSF, granulocyte-colony-stimulating factor; HLH, hemophagocytic lymphohistiocytosis			

AD-ST-33.06 Effective date: 12-Nov-2020

Version 2.0 | Date 24-Oct-2022 | AD-PR-109.02 Effective date: 17-Aug-2020

- Statistical Analysis Plan, Sponsor Sobi AG Protocol Number NI-0501-09 PCN Number 176784
- Overall Survival, defined as the time from the date of first dose to the date of death. Patients without an event will be censored at date of last contact. The analysis start and end dates and the censoring rules are described in the following scheme:

Table 8: Overall Survival

Situation	Outcome (event or censored)	Analysis start date	Analysis end date
No assessments after first infusion	Censored	Start of treatment	Start of treatment + 1
Death for any cause	Event	Start of treatment	Death
Alive at the end of the observation period*	Censored	Start of treatment	Last known alive
* end of study, or premature end of study for the patient (including withdrawal of consent)			

• Survival to HSCT, defined as the time from the date of first dose to the date of death. Patients who receive a HSCT will be censored at that date. Patients who did not receive HSCT will be censored at date of last contact. The analysis start and end dates and the censoring rules are described in the following scheme:

Table 9: Survival to HSCT

Situation	Outcome (event or censored)	Analysis start date	Analysis end date
No assessments after first infusion	Censored	Start of treatment	Start of treatment + 1
Death for any cause	Event	Start of treatment	Death
Alive at HSCT	Censored	Start of treatment	HSCT date
Alive without having received HSCT	Censored	Start of treatment	Last known alive date

Protocol Number NI-0501-09 PCN Number 176784

[figure not shown]
Statistical Analysis Plan, Sponsor Sobi AG

• Survival post HSCT, defined as the time from date of HSCT to the date of death. Patients without an event will be censored at date of last contact. Patients who do not proceed to HSCT will be excluded from this analysis. The analysis start and end dates and the censoring rules are described in the following scheme:

Table 10: Survival post HSCT

Situation	Outcome (event or censored)	Analysis start date	Analysis end date
Death for any cause	Event	Date of HSCT	Death
Alive at the end of the observation period* Censored Date of HSCT Last known alive date			
* end of study, or any time during follow-up period (including withdrawal of consent)			

- HLH Reactivation = any adverse event in the following preferred term (PT) (PT code):
 - Condition Aggravated (10010264)
- Graft failure = any adverse event in at least one of the following PTs (PT code):
 - Transplant failure (10060872)
 - Engraft failure (10068081)
 - Bone marrow transplant rejection (10048396)
 - Transplant rejection (10044439)
 - Complications of bone marrow transplant (10010162)
 - Graft loss (10048748)
- Event-free survival = time from HSCT to date of (whichever occurs first): death from any cause, graft failure, HLH reactivation. The analysis start and end dates and the censoring rules are described in the following scheme:

Situation	Outcome (event or censored)	Analysis start date	Analysis end date	
At least one event, i.e. graft failure, HLH reactivation, death for any cause	Event	Date of HSCT	Date of first event	
None of the events at the end of the observation period*	Censored	Date of HSCT	Last known alive	
* end of study, or any time during follow-up period (including withdrawal of consent)				

Table 11: Event-Free Survival

• Duration of Response (i.e. maintenance of response achieved at any time during the study until EOT) is defined as the total elapsed time from achievement of first Overall Response to first loss of response, pending the duration of this response is at least 4 days. If the first observed response does not last for at least 4 days, then the next response period will be considered. Similarly, loss of response should persist for at least 4 days, otherwise the next loss of response period will be considered. Patients who are in response at EOT will be censored at that date. Patients who do not achieve at least HLH improvement once between the date of first dose and EOT will be excluded from the analysis.

The analysis start and end dates and the censoring rules for calculation of duration of response are described in the following scheme:

Situation	Outcome (event or censored)	Analysis start date	Analysis end date
Maintained loss of overall response	Event	Date of first response ²	Date of loss of overall response ²
Death for any cause	Event	Date of first response ²	Date of death
In response at the end of the observation period ¹	Censored	Date of first response ²	Last known response

Table 12: Duration of Response

AD-ST-33.06 Effective date: 12-Nov-2020

¹ end of treatment without conditioning, or start of conditioning for HSCT, or early termination (including withdrawal of consent);

[figure not shown]
² last for at least 4 days

- Cumulative Duration of Response = Total time in response from the first achievement of an Overall Response until HSCT conditioning (or EOT if the patient did not have HSCT performed). Considering patients who achieve a response, lost that response, and then achieve it subsequently, the total time in response will be calculated by adding together these separate periods in response. Patients who do not achieve response at least once between the date of first dose and the time of conditioning start are excluded from the analysis.
- Percent days in response = Cumulative response duration divided by number of days from first infusion until HSCT conditioning (or EOT if the patient did not have HSCT performed).

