6.3.5 Additional HLH treatments

The administration of additional HLH treatments (e.g., etoposide, T-cell depleting agents) will be allowed concomitantly with emapalumab.

In a patient in whom an HLH worsening or no initial response has been observed after an increase of emapalumab dose to 6 mg/kg on SD3, at SD6 the Investigator may consider the therapeutic option of adding an alternative HLH treatment while continuing emapalumab.

Benefit/risk of administering an additional HLH treatment (with or without emapalumab dose increase) must be assessed, taking into consideration e.g. possible drug toxicities, trends of relevant clinical/laboratory parameters in that individual patient, extent of past response to conventional HLH therapy (if a second-line patient).

The administration of an additional HLH treatment is also allowed later during the course of emapalumab treatment in case of unsatisfactory HLH control, provided that emapalumab has been administered at a dose of 6 (or 10 mg/kg if the Investigator decided to do so) for at least 2 infusions.

Unsatisfactory HLH control is defined as follows:

- patients who have not achieved or maintained a disease control and general conditions that would allow to proceed to transplant
- patients who present a clinically relevant worsening.

If an additional HLH treatment is needed, etoposide is the drug of choice, unless there is evidence indicating that an alternative agent should be selected. The rationale for administration of additional HLH treatments (including the choice of an agent alternative to etoposide, if applicable) has to be documented in the patient's medical file and in the Dose Notification Form (Appendix E).

At any time, the Investigator can decide to discontinue emapalumab treatment and opt for a different HLH regimen in the patient's best interest, as described in the Section 10.1.3.

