8.2.1. Overall Survival

Overall Survival, Survival to HSCT and Survival post HSCT (Section 6.1.9.4) will be analysed using a descriptive time-to-event approach including Kaplan-Meier curves.

[figure not shown]
Summaries will include the number and rates of patients experiencing the event and the number of censored observations; the median and 95% confidence interval, and lower quartile and upper quartile estimates of time-to-event; survival estimates at specified timepoints; and the median, minimum and maximum follow-up time in months.

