14.3. Planned Figure Descriptions

The following are planned summary figures for protocol number NI-0501-09. The figure numbers and page numbers are placeholders only and will be determined when the figures are produced.

Table 17: Planned Figures

Figure Number	Figure Title/Summary	Population
14.4.1.1	Kaplan-Meier Graph of Overall Survival	All Treated Pop
14.4.1.2	Kaplan-Meier Graph of Survival to HSCT	All Treated Pop
14.4.1.3	Kaplan-Meier Graph of Survival post HSCT	All Treated Pop
14.4.2	Kaplan-Meier Graph of Event-free Survival	All Treated Pop
14.4.3	Cumulative Incidence Graph of Time to Response	All Treated Pop
14.4.4	Kaplan-Meier Graph of Duration of Response	All Treated Pop
14.4.5.1	Box and Whisker Plots of Clinical Biochemistry Results	All Treated Pop
14.4.5.2	Box and Whisker Plots of Hematology Results	All Treated Pop
14.4.5.3	Box and Whisker Plots of Coagulation Results	All Treated Pop

[figure not shown]
15. Tables, Listings, and Listing Shells

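### Survival to HSCT is estimated by Kaplan-Meier with censoring at transplant, a competing event, so the curve does not give the proportion of treated patients who die before HSCT

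*SAP*

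**What the plan says.** SAP 6.1.9.4 defines Survival to HSCT as time from first dose to death. Two censoring rules matter: "Patients who receive a HSCT will be censored at that date", and "Patients who did not receive HSCT will be censored at date of last contact". Table 9 repeats them. The protocol (7.1) lists survival to HSCT within Overall Survival and gives no censoring rule.

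SAP 8.2.1 says "Overall Survival, Survival to HSCT and Survival post HSCT (Section 6.1.9.4) will be analysed using a descriptive time-to-event approach including Kaplan-Meier curves". The outputs are the median with its confidence interval, the quartiles, and "survival estimates at specified timepoints"; the timepoints are not named. The only planned figure for the endpoint is "Kaplan-Meier Graph of Survival to HSCT" (SAP 14.3, Table 17). No competing-risk estimator is named for it.

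Two planned outputs bear directly on the point. Section 8.2.1 also states "Summaries will include the number and rates of patients experiencing the event and the number of censored observations", and 8.2.8 gives the count and percentage of patients who proceed to HSCT.

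On the role of transplant, Protocol 3.3 foresees treatment up to the start of conditioning, for no more than 6 months. It sets a 4-week minimum, subject to the patient's condition and donor availability. Protocol 1.1 describes HSCT as necessary for cure.

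**The concern.** Once a patient has been transplanted, that patient can no longer die before transplant. Kaplan-Meier censoring treats the patient as still exposed to that outcome and represented by those not yet transplanted. As transplants accumulate, each further pre-transplant death is spread over a shrinking risk set and counts for more than one treated patient. The complement of the curve (1-KM) then exceeds the actual cumulative incidence whenever transplants precede some of the deaths.

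The natural question for a bridging treatment is how many treated patients die before they reach transplant, and when. A reader who takes a timepoint estimate from this curve as the answer would get too pessimistic a figure. The tail would rest on few patients, because untransplanted patients are followed for a year after the last infusion (Protocol 3.4) while the others have left the risk set. The naive and experienced subgroups (SAP Table 3) thin it further.

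**Working it through.** **The plan's own figure.** There is none to reproduce. The documents give no death rate, HSCT rate or median for this endpoint. Every rate below is an assumption.

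**Set-up.** Let λ be a constant monthly hazard of death before HSCT. Let μ be a constant monthly hazard of HSCT starting at s = 0.92 months (28 days / 30.4375), from the 4-week minimum in Protocol 3.3. At time T > s:

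- 1-KM(T) = 1 − exp(−λT)
- Cumulative incidence of death before HSCT = 1 − exp(−λs) + exp(−λs) × λ/(λ+μ) × [1 − exp(−(λ+μ)(T−s))]
- Cumulative incidence of HSCT = exp(−λs) × μ/(λ+μ) × [1 − exp(−(λ+μ)(T−s))]

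**One case in full.** Target 15% dead before HSCT and 60% transplanted by T = 6. Solving gives λ = 0.0418 and μ = 0.2235.

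- exp(−0.0418 × 0.92) = 0.962, so 3.8% die before week 4.
- 1 − exp(−0.2653 × 5.08) = 0.740.
- Death: 0.038 + 0.962 × 0.1576 × 0.740 = 0.150.
- HSCT: 0.962 × 0.8424 × 0.740 = 0.600.
- 1-KM: 1 − exp(−0.0418 × 6) = 0.222.

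**Range over the unknown HSCT rate** (month 6, 15% dead before HSCT):

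| Transplanted by month 6 | Cumulative incidence of death | 1-KM | Excess (points) |
|---|---|---|---|
| 30% | 15% | 17.5% | 2.5 |
| 45% | 15% | 19.4% | 4.4 |
| 60% | 15% | 22.2% | 7.2 |
| 75% | 15% | 27.3% | 12.3 |

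With 10% dying, 1-KM is 11.6% at 30% transplanted and 16.2% at 70%. With 20% dying, it is 23.5% and 35.0%.

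**Does it need transplant to depend on risk?** Simulation of 200,000 patients, 65% with controlled disease and 35% without, HSCT from 0.92 months, month 6. Hazards are monthly and assumed. The last column is the exact death risk if nobody could be transplanted.

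| Scenario | Controlled: death, HSCT | Uncontrolled: death, HSCT | 1-KM | Cumulative incidence | No-transplant risk |
|---|---|---|---|---|---|
| No link | 0.05, 0.35 | 0.05, 0.35 | 25.6% | 14.8% | 25.9% |
| Controlled transplanted sooner | 0.02, 0.35 | 0.10, 0.10 | 27.6% | 17.4% | 23.1% |
| Uncontrolled transplanted sooner | 0.02, 0.10 | 0.10, 0.45 | 18.9% | 14.6% | 23.1% |

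1-KM exceeds the cumulative incidence in all three. It matches the no-transplant risk, up to simulation error, only when there is no link. Selection pushes it above or below that risk.

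**At the trial's size.** An illustrative set of 34 patients has 6 deaths before HSCT at evenly spaced times from 0.5 to 8 months, 24 transplants from 1.2 to 7 months, and 4 patients followed beyond month 12. The risk sets at the six deaths are 34, 29, 22, 15, 8 and 5.

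- Month 6 (four deaths): 1-KM = 1 − (33/34)(28/29)(21/22)(14/15) = 16.5%, against 4/34 = 11.8%.
- Month 12 (all six): multiplying further by (7/8)(4/5) gives 1-KM = 41.6%, against 6/34 = 17.6%.

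With 10 deaths and 20 transplants arranged the same way, 1-KM at month 12 is 56.8% against 10/34 = 29.4%. The curve then yields a median, although fewer than a third of patients died before HSCT.

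**The case against.** The strongest reply is that the SAP never calls the complement of this curve the chance of dying before HSCT. It plans a survival curve censored at HSCT, which is a recognised cause-specific summary, and only for Time to Response (8.2.5) does it present 1-KM as a cumulative incidence. It also plans the crude number and rate of deaths before HSCT (8.2.1), the HSCT count (8.2.8), and an Overall Survival analysis that is not censored at HSCT (Table 8). With little loss to follow-up, the crude rate is close to the final cumulative incidence. All of this stands. It narrows the gap to the time course, the timepoint estimates and their intervals; it does not make the curve, median or quartiles answer the bridging question.

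Three stronger readings are tempting but not supported.

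- **That transplant goes mainly to patients with controlled disease.** A reader might infer this from "patients who have not achieved or maintained a disease control and general conditions that would allow to proceed to transplant" (Protocol 6.3.5), but that text defines when additional HLH treatment is allowed. Donor availability also drives timing (Protocol 3.3), and patients in maintained Complete Response may wait beyond 12 weeks (5.3). The conclusion does not need this premise.
- **That the curve validly shows mortality in a world without transplant.** That holds only if transplant timing is unrelated to risk. Any dependence biases this reading too.
- **That the curve would mislead the iDMC.** The iDMC reviews fatal events before transplant in treatment-naïve patients under its own charter (Protocol 3.6), and the SAP plans no interim analysis (4.2). Nothing links that review to this curve.

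**Conclusion.** The point holds in a limited form. Survival to HSCT, as planned, censors at a competing event, so its curve and the estimates drawn from it are not the proportion of treated patients who die before HSCT. Read as that proportion they are too high, and this follows from the estimator without any assumption about who is transplanted.

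How much too high cannot be fixed from the documents. Under constant hazards, HSCT from week 4 and 15% dead before HSCT by month 6, the excess runs from 2.5 points (30% transplanted) to about 12 points (75%), and it grows later. Larger figures, such as 32% against 15%, might be inferred by letting transplant start on day 0 and having 90% of patients either dead or transplanted by month 6. Nothing in the documents supports those settings, and with HSCT from week 4 the same rates give 27%. If few patients reach HSCT, the excess is small.

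The endpoint is a descriptive, supportive secondary without a p-value. The primary response test is unaffected.

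**What to change.** Add to SAP 8.2.1 the Aalen-Johansen cumulative incidence of death before HSCT, with HSCT as the competing event, and of HSCT, with death as the competing event. Give both with 95% confidence intervals at named timepoints, and add the matching figure to Table 17. Use these for any statement about the probability of dying before, or reaching, transplant. Keep the Kaplan-Meier curve and label it as censored at HSCT.

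The cost is one extra table and one figure. The dates of first infusion, HSCT, death and last contact are already collected, so no new data are needed.

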Abbreviations: ADAs, anti-drug antibodies; AE, adverse event; ALP, alkaline phosphatase; ALT, alanine transaminase, aPTT, activated partial thromboplastin time; AST, aspartate transaminase; CBC, complete blood count; cm, centimeter; CMV, cytomegalovirus; CRP, C-reactive protein; D, day; EBV, Epstein-Barr virus; EOT, end of treatment; yGT, gamma glutamyl transferase; HSCT, hematopoietic stem cell transplantation; ICF, informed consent form; IFNy, interferon gamma; INR, International normalized ratio; LDH, lactate dehydrogenase; LUC, large unstained cells; mo, month; PD, pharmacodynamic; PK, pharmacokinetic; PT, prothrombin time; QOL, quality of life; SAE, serious adverse event; TB, tuberculosis; US, ultrasound; UV, unscheduled visit; WD, withdrawal visit; wk, week; yr, year CBC: white blood cells and differential, red blood cells, hemoglobin, hematocrit, platelets, LUC (as available). Coagulation: aPTT (time and/or ratio), PT and/or INR, d-Dimers, fibrinogen. Biochemistry: glucose, CRP, ferritin, triglycerides, liver (AST, ALT, yGT, LDH, ALP, bilirubin) and renal function (albumin, creatinine and urea). Urinalysis: glucose, blood, protein and/or albumin, leukocytes, ketones, pH, gravity

^{*} Follow-up pre-HSCT: if HSCT is not planned, patient will directly follow the Schedule of Assessment indicated for Follow-up after last emapalumab infusion

^b **EOT**: indicated as reference only, refer to Table 1

Fre Conditioning visit: may be combined with EOT visit (if not more than 2 days apart). The EOT schedule of assessments has to be applied

d Allowed time-windows: a ±2 day window is allowed until D+30 visit. A ±1 week window is allowed for D+60 and D+100 visits. A ±4 week window is allowed for 6-mo and 1-yr visits

e WD (Withdrawal visit): assessments as indicated for last study visit are to be performed in case of premature study discontinuation

f UV (Unscheduled visit): assessments to be performed as clinically indicated

F Physical examination: includes as a minimum: spleen and liver size (by abdominal palpation), height/length (at Pre-Conditioning and 6 month visit only) and neurological examination

h Post-HSCT outcome: applies to patients who undergo HSCT. Includes engraftment rate, donor chimerism achieved (as available), incidence of acute and chronic graft versus host disease

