8.6.2 Follow-Up Post-HSCT (or After Last Emapalumab Infusion)

The following assessments will be performed at weekly visits after either HSCT or last emapalumab infusion (as applicable) until Day 30, and subsequently at Day 60, Day 100, and Month 6:

(In addition to the below, in patients undergoing HSCT, PK/PD samples will be collected at Day 3 post-transplant).

Clinical Assessment:

- Vital signs, including body temperature, heart rate, blood pressure, and oxygen saturation
- Physical examination, including as a minimum, spleen and liver size (by abdominal palpation), height/length (at 6 month visit only) and neurological examination
- Post HSCT outcome, if applicable
- Survival
- QOL questionnaires PedsQL[™], Pediatric Quality of Life Inventory[™] and BASES if HSCT is performed (at Day 30, Day 100 and Month 6 visits)

Laboratory:

- CBC with differential count (including large unstained cells count, whenever performed as routine)
- Coagulation tests: activated partial thromboplastin time and/or ratio, prothrombin time and/or INR, D-dimers, and fibrinogen

Study NI-0501-09 NI-0501 in Primary HLH Page 56 of 92

- Biochemistry: glucose, ferritin, CRP, liver function (AST, ALT, γGT, LDH, ALP, bilirubin), renal function (albumin, creatinine and urea) and triglycerides (fasting whenever possible)
- Urinalysis: glucose, blood, protein and/or albumin, leucocytes, ketones, pH, gravity

Search for infections:

- TB by PCR in any relevant specimen, as clinically indicated, at minimum at D+30, D+60, D+100, 6 month and 1 year/WD visits; until serum levels of emapalumab are no longer detectable
- Infection search & monitoring according to the patient's clinical presentation – in case of suspicion of infection

Imaging:

- Chest X-ray in case of clinical suspicion of pulmonary infection or to monitor existing abnormalities
- Abdominal ultrasound with spleen longitudinal measure (at Day 100 visit only)

Safety:

 Recording of any AEs occurred since last visit until serum levels of emapalumab are no longer detectable. After elimination of emapalumab only SAEs will be reported.

PK:

 Emapalumab concentrations (if serum levels of emapalumab were still measurable at the previous visit). Also at D+3 after HSCT, if performed

PD:

 CXCL9, CXCL10, sCD25, total IFNy (if serum levels of emapalumab were still measurable at the previous visit; then only if clinically indicated). Also at D+3 after HSCT, if performed

Immunogenicity:

Assessment for ADAs (at Day 100 visit only)

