For a given AE, the assessment of its intensity should reflect the highest grade (on the three-point scale mentioned above) reported during its course (except when the intensity of a pre-treatment AE increases after treatment initiation, as indicated above).

The relationship of AEs to the IMP will be assessed by the Investigator using a "Yes/No" classification. A "Yes" relationship infers that there is a reasonable suspected causal relationship to the IMP. The

Study NI-0501-09 NI-0501 in Primary HLH Page 59 of 92

expression "reasonable causal relationship" is meant to convey that there are facts, evidence or arguments to suggest a causal relationship. In this study, emapalumab is the only IMP.

Specific situations:

- Common HLH signs and symptoms (e.g., anemia, neutropenia, thrombocytopenia, pancytopenia, splenomegaly, hepatomegaly) will not be reported as separate AEs unless clearly attributed to a cause different from HLH, and the verbatim term should indicate the cause.
- If changes in the above mentioned HLH signs and symptoms indicate HLH worsening or reactivation, worsening or reactivation will be reported as an AE.
- Fever will only be reported when not linked to an identified cause with the highest temperature considered during the period. If it is a recurrent fever it can be entered as intermittent fever with no need to specify the temperature (the intensity should be a reflection of the highest temperature observed). If fever is considered as a sign of a confirmed infection or of HLH worsening or reactivation, only the diagnosis should be reported as an AE, and not `fever`.
- Viral load positivity, in particular for EBV, CMV and adenovirus, and evolution will be collected on a dedicated eCRF module.
- Active infections will be reported as AEs, indicating whether constituting a primary infection or a reactivation (whenever possible). Pathogen positivity and evolution will be collected in a dedicated eCRF module.
- Expected effects of conditioning (i.e., pancytopenia during conditioning and until engraftment) will not be reported.

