14.2.1.1.6	Sensitivity analysis 5: Overall Response at EOT or Week 8 (whichever occurs earlier) with patients deemed as having a protocol deviation impacting statistical analysis removed	Evaluable Pop Without Major PDs	16.2.6.3
14.2.1.1.7	Supplementary Analysis: Overall Response at EOT or Week 8 (whichever occurs earlier) – Modified Definition	All Treated Pop	16.2.6.3
14.2.1.2	Overall Response Components: Complete Response, Partial Response, HLH Improvement, No Response	All Treated Pop, Evaluable Pop	16.2.6.3
14.2.1.3.1	Evolution of Clinical Signs Characterizing HLH Disease - Part 1	All Treated Pop, Evaluable Pop	16.2.6.1.1, 16.2.9.3.
14.2.1.3.2	Evolution of Clinical Signs Characterizing HLH Disease - Part 2	All Treated Pop, Evaluable Pop	16.2.9.4
14.2.2.1	Overall Survival	All Treated Pop, Evaluable Pop	16.2.6.2
14.2.2.2	Survival to HSCT	All Treated Pop, Evaluable Pop	16.2.6.2
14.2.2.3	Survival post HSCT	All Treated Pop, Evaluable Pop	16.2.6.2
14.2.3	Event-free Survival post HSCT	All Treated Pop, Evaluable Pop	16.2.6.2
14.2.4.1	Duration of Response	All Treated Pop, Evaluable Pop	16.2.6.2
14.2.4.2	Cumulative Duration of Response for Patients Achieving Overall Response	All Treated Pop, Evaluable Pop	16.2.6.1.1, 16.2.6.1.2, 16.2.6.1.3, 16.2.6.1.4.

premier research

Table Number	Table Title / Summary	Population(s)	Supporting listing
14.2.5	Time-to-Response	All Treated Pop, Evaluable Pop	16.2.6.2
14.2.6	Investigator Assessment of Clinical Response	All Treated Pop, Evaluable Pop	16.2.6.4
14.2.7.1	Summary of Dexamethasone Daily Dose (mg/m ²) Over Time	All Treated Pop, Evaluable Pop	16.2.5.3
14.2.7.2	Glucocorticoids Reduction	All Treated Pop, Evaluable Pop	16.2.6.3
14.2.7.3	Patients Proceeding to HSCT	All Treated Pop, Evaluable Pop	16.2.6.3
14.2.8.1	Summary of PedsQL Total Scale Score (Parent Reports) and Change from Baseline by Questionnaire Age Group	All Treated Pop, Evaluable Pop	16.2.6.8
14.2.8.2	Summary of PedsQL Physical Health Summary Score (Parent Reports) and Change from Baseline by Questionnaire Age Group	All Treated Pop, Evaluable Pop	16.2.6.8
14.2.8.3	Summary of PedsQL Psychosocial Health Summary Score (Parent Reports) and Change from Baseline by Questionnaire Age Group	All Treated Pop, Evaluable Pop	16.2.6.8
14.2.8.4	Summary of PedsQL Physical Functioning Scale Score (Parent Reports) and Change from Baseline by Questionnaire Age Group	All Treated Pop, Evaluable Pop	16.2.6.8

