16.2.6.3	Overall Response, Glucocorticoids Reduction, and Ability to Proceed to HSCT	All Treated Pop
16.2.6.4	Investigator Assessment of Clinical Response	All Treated Pop
16.2.6.5	HSCT	All Treated Pop
16.2.6.6	Post-HSCT Outcome	All Treated Pop
16.2.6.7	Survival Assessment	All Treated Pop
16.2.6.8	PedsQL Parent Reports	All Treated Pop
16.2.6.9	PedsQL Child Reports	All Treated Pop
16.2.6.10	BASES Parent Reports	All Treated Pop
16.2.6.11	BASES Nurse Reports	All Treated Pop
16.2.7.1.1	Adverse Events	All Treated Pop
16.2.7.1.2	Adverse Events occurring prior to HSCT conditioning	All Treated Pop
16.2.7.1.3	Adverse Events occurring post HSCT conditioning	All Treated Pop
16.2.7.2	Serious Adverse Events	All Treated Pop
16.2.7.3	Adverse Events Leading to Withdrawal of Study Drug	All Treated Pop
16.2.7.4	Deaths	All Treated Pop
16.2.7.5	Tuberculosis	All Treated Pop
16.2.7.6	Adenovirus, Epstein-Barr Virus, Cytomegalovirus	All Treated Pop
16.2.7.7	Other Specific Infections	All Treated Pop
16.2.8.1	Clinical Chemistry Results	All Treated Pop
16.2.8.2	Hematology Results	All Treated Pop
16.2.8.3	Coagulation Results	All Treated Pop

AD-ST-33.06 Effective date: 12-Nov-2020

Version 2.0 | Date 24-Oct-2022 | AD-PR-109.02 Effective date: 17-Aug-2020

Listing Number	Listing Title / Summary	Population(s)
16.2.8.4	Urinalysis Results	All Treated Pop
16.2.8.5	Pregnancy Test Results	All Treated Pop
16.2.9.1	Vital Signs	All Treated Pop
16.2.9.2	ECG Results	All Treated Pop
16.2.9.3	Physical Examination Results	All Treated Pop
16.2.9.4	Neurological Examination Results	All Treated Pop
16.2.9.5	Hospitalization	All Treated Pop
16.2.9.6	Abdominal Ultrasound	All Treated Pop
16.2.9.7.1	Chest Examinations	All Treated Pop
16.2.9.7.2	Brain and Cranial Examinations	All Treated Pop
16.2.9.8.1	CSF Analysis Results	All Treated Pop
16.2.9.8.2	Serum Concentration of Emapalumab	All Treated Pop
16.2.9.8.3	Pharmacodynamic Measurements	All Treated Pop
16.2.9.8.4	ADA Findings	All Treated Pop
16.2.9.9	Transfusion	All Treated Pop
16.2.9.10	List of Patients Who Were Affected by COVID-19	All Treated Pop

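### Event-free survival counts one unspecific transplant-complication AE term as graft failure without any confirmation

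*SAP*

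**What the plan says.** SAP Section 6.1.9.4 sets the endpoint out as "Event-free survival = time from HSCT to date of (whichever occurs first): death from any cause, graft failure, HLH reactivation". SAP Table 11 takes the date of the first such event as the analysis end date. The protocol (Section 7.1) names event-free survival as a secondary endpoint but does not define its events, so the SAP definition is the operative one.

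The graft-failure component is "Graft failure = any adverse event in at least one of the following PTs (PT code", followed by six terms. Five refer to transplant or engraftment failure, rejection, or loss of the graft. The remaining one is "Complications of bone marrow transplant (10010162". No verbatim review, adjudication or supporting evidence is required for any of the six.

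The protocol also collects a separate post-transplant outcome assessment. Table 2, footnote h, describes it: "Includes engraftment rate, donor chimerism achieved (as available), incidence of acute and chronic graft versus host disease". Sections 8.6.2 ("Post HSCT outcome, if applicable") and 8.6.3 schedule it at the post-transplant visits through 1 year. In the SAP these data appear only as Listing 16.2.6.6, "Post-HSCT Outcome". The results table, 14.2.3 ("Event-free Survival post HSCT"), cites the time-to-event listing, 16.2.6.2, as its source.

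**The concern.** Graft failure is a specific outcome, and five of the six terms match it. The sixth names a complication of the procedure without saying that the graft failed. If a site reports a transplant complication in vague words and the coder assigns this term, the algorithm records graft failure on that date, whatever happened to the graft.

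The study has information that could settle such a case, namely engraftment status and, where available, chimerism, but the SAP does not consult it. At stake is the accuracy of a named secondary endpoint that bears on the stated objective of long-term outcome. With few transplanted patients, one wrong event is visible on the Kaplan-Meier curve.

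**Working it through.** **No plan figure to reproduce.** The documents give no event-free rate, event count or number transplanted. The check is mainly of the text, with a bounded illustration.

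**Step 1: does the rule admit a non-failure?** Inputs: the six-term list and the event-free survival definition (SAP 6.1.9.4) and the event-date rule (SAP Table 11).
- An AE coded to the complications term satisfies the graft-failure definition with no further condition.
- Graft failure is a component of event-free survival, so the patient has an event.
- If it comes first, its date becomes the analysis end date.

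Nothing in this chain asks whether the graft failed.

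**Step 2: could an existing check catch it?** SAP Section 10.8 lists conditioning and transplant dates, stem cell source, graft manipulation and donor type, but no engraftment result. Listing 16.2.6.6 shows the outcome data but feeds no derivation. A reader could spot a discrepancy by hand; the reported estimate would not change.

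**Step 3: can real graft failures be missed?** Set the reporting rules side by side.
- Protocol 9.2.1: "Expected effects of conditioning (i.e., pancytopenia during conditioning and until engraftment) will not be reported". This exempts the expected cytopenia, not a diagnosis of graft failure.
- Protocol 9.2.4: a laboratory abnormality that leads to a new clinical diagnosis is reported as that diagnosis.
- Protocol 9.2.2: an event is serious if, for example, it is life-threatening, prolongs hospitalization or is an important medical event. The exemption for short post-transplant stays does not apply once a new diagnosis is confirmed.
- Protocol 9.2.1 and 8.6.3: after emapalumab is eliminated, SAEs are still collected to the 1-year visit.

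Overt graft failure should therefore reach the AE database. A miss would need a site reporting failure, or a non-serious or chimerism-only finding. That is possible but unlikely.

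**Step 4: size of one false event.** Assume n transplanted patients, complete follow-up, and a misclassified patient with no other component event. The change in the event-free proportion is 1/n:

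| n (assumed) | 1/n |
|---|---|
| 15 | 6.7 points |
| 20 | 5.0 points |
| 25 | 4.0 points |
| 30 | 3.3 points |

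Illustration at n = 25, with a true event-free count of 20 (also assumed) and exact (Clopper-Pearson) 95% intervals:
- No misclassification: 20/25 = 80.0% (59.3 to 93.2).
- One false event: 19/25 = 76.0% (54.9 to 90.6).
- Two false events: 18/25 = 72.0% (50.6 to 87.9).

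If the patient later dies or has HLH reactivation within the same period, the proportion at the end of that period is unchanged and only the event time moves earlier.

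**The case against.** The strongest case against the point has four parts.

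*Scope of the term.* The dictionary definition and coding rules are not in the documents, so the breadth of the complications term is inferred from its wording. AEs reported under a specific diagnosis would be coded to their own terms. This stands as a limit: the documents show that a vaguely worded AE could be counted, not how often it would be.

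*AE records suit a time-to-event endpoint.* They carry onset dates. Footnote h describes no graft-loss field, chimerism threshold or failure date, and chimerism is collected only as available. This stands. A reader might infer that the outcome data should replace the AE terms as the source of graft failure; that would rest on fields the documents do not show.

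*Missed failures.* A reader might also infer that the endpoint routinely misses primary graft failure, because cytopenia before engraftment is exempt from reporting and the outcome data are unused. The documents do not support this: the exemption covers only expected conditioning effects, and the diagnosis and SAE rules still require overt graft failure to be reported.

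*Limited impact.* Event-free survival is a single-arm Kaplan-Meier description with no p-value. Overall survival and survival after transplant are analysed separately and are untouched. This stands and keeps the point modest.

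None of these explains why an AE that need not be graft failure should count as one without a check.

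**Conclusion.** The point holds for one preferred term. As written, the SAP can turn a transplant complication other than graft failure into an event-free survival event and fix its date, with no confirmation step.

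For an assumed 15 to 30 transplanted patients, one such error moves the event-free proportion by at most 6.7 to 3.3 points. This rests on complete follow-up and on the patient having no other component event. It is a ceiling per patient, not an expected bias, because the number of misclassified patients cannot be known from the documents. Missed graft failures are a minor, secondary risk that would push the estimate the other way. The primary endpoint and its test are unaffected.

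**What to change.** Amend SAP 6.1.9.4 before database lock:

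1. Keep the five failure, rejection or loss terms as graft-failure events without further conditions.
2. Count an AE coded to the complications term only if case review of the AE verbatim and the post-transplant outcome data (engraftment, and chimerism where available) confirms graft failure. Use the AE onset date as the event date.
3. In the same review, compare the post-transplant outcome data with the AE data. Where non-engraftment is recorded without a matching AE, query the site.
4. Record each decision and its reason, so that the classification is fixed before results are produced.

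The SAP already plans a data review meeting before lock, and it already asks for manual checking of some ambiguous steroid codings (Table 14), so the step fits its practice. No new data collection is needed. The cost is a few lines of SAP text and a short review of a few AEs.
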